### Risks of Incidental Findings

Since the MRI methods being tested are experimental, the MRI images will not be formally reviewed for incidental findings. However, if there is something that is of concern to the PI, then the PI will approach the IRB for guidance on how to proceed on a case-by-case basis. The consent will clearly state that the MRI images will not be evaluated for incidental imaging findings.

**Protection Against Risk:** Study visits and informed consent will be performed in private rooms, to prevent potential loss of confidentiality. All MRI will be conducted in the presence of a qualified healthcare professional trained and certified in the American Heart Association's Advanced Cardiac Life Support (ACLS) training. This individual will be present in the MRI suite during Xe administration and will monitor all aspects of the subjects well-being and record any transient CNS effects and adverse events should they occur. The subject will be monitored continuously by an MRI-compatible pulse oximeter, recording both heart rate and oxygen saturation. Subjects may discontinue the study at any time. The MRI suite is

also equipped with a safe source of supplemental oxygen that can be provided if needed for patients with pulmonary disease to maintain O2 saturation. All subjects will receive a 24-hour follow-up phone call to check for any symptoms or adverse effects. Any symptoms or effects will be recorded, regardless of their suspected association with Xe MRI.

Extraordinary care will be taken to ensure that all patient data remains confidential and any information is de-identified prior to publication or presentation. All study personnel will have completed their institution's mandatory training in human subjects research and protecting PHI.

## Potential Benefits to Subjects

We anticipate no direct benefit to subjects as a result of participating in the study, since our primary emphasis is to collect a range of MR images and develop interpretation of these results over time. However, it is conceivable that either the anatomical H scans or Xe MR scans may reveal an incidental pathology that requires medical attention. Such a finding could benefit the subject because it will be found earlier than would likely be the case during the subject's normal medical care. Any such findings will be immediately communicated to the subject and his/her physician and all associated records of the study will be made available to them for any further work-ups. The potential benefit of this research is in the noninvasive diagnosis of PAH, which would obviate the need for invasive RHC in these patients.

## 11. Costs to the Subject:

There are no additional costs to the subject for the MRI examination. Subjects will be compensated \$100.00 for travel/parking and time for each study visit via a ClinCard. This does not include the screening visit.

## 12. Data Analysis & Statistical Considerations:

### Sample size

Our sample size calculation is based on testing whether the proposed diagnostic test based on Xe MRI has accuracy comparable to imaging diagnostic procedures in clinical practice, such as mammography. To this end, we propose to test the hypotheses H0: AUC = 0.72 vs. H1: AUC > 0.85, where AUC is a summary measure of diagnostic accuracy obtained as the area under the receiver operating characteristic (ROC) curve which displays the tradeoff between sensitivity and specificity for our proposed Xe MRI based diagnostic test. Here AUC = 0.72 represents a moderately accurate test while AUC = 0.85 represents accuracy comparable to clinical mammography. Based on a one sided, one sample test with variances approximated using the binormal model, we estimate a minimum sample size of 46 normals and 46 with disease will be required to test the above hypotheses at a significance level of 5% with 80% power.

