#### **4. Design & Procedures:**

This study seeks to deploy several forms of Xe MRI contrast as well as emerging conventional proton MRI techniques for imaging lung structure and perfusion. Specifically, the Xe MRI scans will provide 3D images of ventilation and gas exchange, and spectroscopic indices will be evaluated to test gas exchange dynamics with high temporal resolution. The conventional H MRI scans will include a free-breathing ultra-short echo time (UTE) scan that provides images similar to that of a CT scan. The overall aims of the study are as follows:

**Aim 1. Perform Xe MRI scans in cohorts of patients with PVD, isolated left sided heart failure and isolated lung disease:**

- 1.1 Deploy and optimize Xe gas exchange MR spectroscopy and imaging, Xe ventilation MRI, structural H UTE MRI, and breath-hold H perfusion MRI.
- 1.2 Conduct comprehensive H-Xe MRI in 10 patients with pure PAH
- 1.3 Conduct comprehensive MRI in 10 patients with pure left heart failure
- 1.4 Conduct comprehensive MRI in 10 patients with pure lung disease but no pulmonary hypertension
- 1.5 Conduct comprehensive MRI in 5 patients with Chronic thromboembolic pulmonary hypertension (CTEPH) pre and post PTE surgery.

**Aim 2. Develop diagnostic criteria for optimizing the sensitivity and specificity of Xe MRI for the diagnosis of PVD:**

- 2.1 Develop quantification/scoring methods based on PAH, left heart disease, and lung disease MRI
- 2.2 Develop reader training materials and train 3 expert readers
- 2.3 Begin prospective recruitment of 92 patients undergoing right heart catheterization for evaluation of PAH or other cardiac or pulmonary disease for MRI scans. These patients may be asked to return for a second scan in the study, at a time no earlier than 48hr after their last xenon dose.

**Aim 3. Perform a larger, single-blind study testing the diagnostic accuracy of Xe MRI for diagnosis of PVD:**

- 3.1 Trained readers will evaluate Xe MRI, while blinded to the subject's disease state and will determine the presence and severity of PVD
- 3.2 Diagnostic accuracy of Xe MRI will be compared to the gold standard of hemodynamic and clinical criteria of PAH

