  - 3.2.1 The primary focus of Aim 3 is to compare Xe MRI capability to detect absence/presence of pre/post-capillary PH to the gold standard of RHC
    - a. For this PFTs are not necessary, so they are ancillary
    - b. However, they are a standard way to characterize patients for publications, etc, so we would like to get them if we can. Getting them from the medical record is perfectly adequate for this purpose.
      - i. If PFTs are not available from the medical record, they are not so critical as to prevent us from enrolling the subject. In publications we will simply acknowledge the realities of COVID for this missing data.

This will be a single-blinded, open-label study enrolling volunteers and patients with pure PAH (10 subjects), pure left heart disease (10 subjects), pure lung disease (10 subjects) and CTEPH (5 subjects) [Aim 1] followed by a larger cohort of 92 subjects who are undergoing right heart catheterization for evaluation of PAH or other cardiac or pulmonary disease. [Aim 2]. We plan to consent 127 subjects. No subject will be excluded from the study on the basis of gender or ethnicity. Female subjects of childbearing potential will undergo urine pregnancy testing before each MRI. The urine pregnancy test must be negative to continue participating in the study. To refine the precision of Xe MRI for imaging gas transfer efficiency,

we will acquire a hemoglobin level by finger sensor device for each subject testing at each study visit. Informed consent will be obtained before a subject begins any study intervention. Subjects will undergo an approximately hour long comprehensive MRI protocol

Patients with PAH, CTEPH, left heart disease and lung disease will be recruited using minimally restrictive inclusion/exclusion criteria. The Duke Center for Pulmonary Vascular Disease sees approximately 150 patients for evaluation of PAH including CTEPH in a year. For the first phase of the study, whether patients are receiving approved therapies, enrolled in clinical trials, or receiving no therapy, all will be eligible for inclusion in this MRI study. For the second phase of the study, patients who have PAH and receiving approved therapies, patients who are being evaluated for PVD or other cardiac or pulmonary disease will be included in the study.

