### Correlation

Our preliminary Xe MRI studies on patients with PAH, in combination with our previous experience with normals as well as those with other diseases, have helped us formulate quantitative metrics based on Xe MRI studies with high diagnostic potential for PAH. These metrics include the proportion of voxels with low RBC/Gas transfer and the amplitude of the wave seen in Xe MRI based spectroscopy. In Aim 2, our goal is to identify a combination of these metrics which optimally correlates with the current diagnostic standard for PAH which is based on measurements obtained from right heart catheterization, in a training set of 30 patients with and without the disease. The optimal combination will be obtained using discriminant analysis, in which the Xe MRI based metrics will be used as predictors and the diagnosis obtained from right heart catheterization as outcome. To identify the optimal combination and associated thresholds, we will consider all possible combinations of predictors, as well as a variety of discriminant analysis techniques, such as linear discriminant analysis and support vector machines. To avoid optimistic bias from overfitting, we will use leave out one cross validation to obtain an unbiased estimate of prediction error in the training set, which will be used to rank the most predictive discriminant rules. The actual diagnostic accuracy will be evaluated on a separate validation set of 92 patients in Aim 3.

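### The alternative is written as AUC > 0.85, but 46 + 46 is sized to test AUC against 0.72 with 0.85 as the planning value, so rejection supports only AUC > 0.72

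*Combined protocol and SAP*

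**What the plan says.** Section 12 (Sample size) bases the calculation on "testing whether the proposed diagnostic test based on Xe MRI has accuracy comparable to imaging diagnostic procedures in clinical practice, such as mammography". The next sentence sets the hypotheses: "To this end, we propose to test the hypotheses H 0 : AUC = 0.72 vs. H 1 : AUC > 0.85". The two values are then explained: "Here AUC = 0.72 represents a moderately accurate test while AUC = 0.85 represents accuracy comparable to clinical mammography". The method is "Based on a one sided, one sample test with variances approximated using the binormal model", at 5% significance and 80% power, giving a minimum of 46 subjects without disease and 46 with disease to test the hypotheses just written.

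The other places that describe the accuracy evaluation give no AUC value:

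- Section 4, Aim 3, item 3.2: MRI accuracy "will be compared to the gold standard of hemodynamic and clinical criteria of PAH".
- Section 4, Aim 3, item 3.2.1: the primary focus is to compare "MRI capability to detect absence/presence of pre/post-capillary PH to the gold standard of RHC".
- Section 12 (Correlation): "The actual diagnostic accuracy will be evaluated on a separate validation set of 92 patients in Aim 3".

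The Sample size paragraph is therefore the only quantitative hypothesis in the plan. Nowhere does the plan say that 0.85 is merely the value at which power was computed, or what a rejection would allow the study to conclude.

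**The concern.** The null value and the written alternative do not meet. A true AUC of 0.80, for instance, satisfies neither H0 nor H1. A one-sided, one-sample test with null value 0.72 can show that the AUC exceeds 0.72. It cannot show that the AUC exceeds a higher value that played no part in the test statistic.

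The paragraph also ties the test to the mammography aim and equates 0.85 with mammography-level accuracy. Read literally, rejecting H0 in the 92 validation patients means accepting AUC > 0.85, and hence comparability with mammography. What the sized test excludes is AUC at or below 0.72, the level that the plan itself calls moderate. No success rule or confidence-limit criterion stands between the rejection and the larger claim.

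**Working it through.** **Inputs, all from Section 12 (Sample size).** Null value 0.72; second value 0.85; one-sided α = 0.05 (z = 1.645); power 0.80 (z = 0.8416); binormal variance; 46 per group.

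**Step 1: reproduce 46 + 46.** The plan does not print its variance formula. The usual binormal approximation (Obuchowski) for equal groups is

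V(AUC) = 0.0099 · exp(−A²/2) · [(5A² + 8) + (A² + 8)], with A = 1.414 · Φ⁻¹(AUC).

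- AUC 0.72: A = 0.824, V = 0.1415, √V = 0.3762
- AUC 0.85: A = 1.466, V = 0.0977, √V = 0.3126

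n per group = [1.645 · 0.3762 + 0.8416 · 0.3126]² / (0.85 − 0.72)² = (0.6188 + 0.2631)² / 0.0169 = 0.7778 / 0.0169 = **46.02**.

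This matches the stated 46 (power at 46 + 46 is 79.99%; strict rounding up would give 47). The two-sided version gives 59.2. One-sided variants give 35.7 (variance at 0.85 only), 51.8 (variance at 0.72 only) and 41 (Hanley-McNeil variance). Planning values of 0.84 and 0.86 give 54.8 and 39.0. The figure is therefore the one-sided test of 0.72, powered at exactly 0.85.

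**Step 2: where this test rejects.** The plan does not say which standard error the analysis will use, so both are shown.

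- (i) Null variance: SE = √(0.1415/46) = 0.0555; cutoff = 0.72 + 1.645 · 0.0555 = **0.811**.
- (ii) SE at the observed AUC: solving x − 1.645 · √(V(x)/46) = 0.72 gives x = **0.803**.

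Both cutoffs lie below 0.85, so H0 can be rejected in favour of the written H1 with a point estimate that contradicts H1.

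**Step 3: how often it rejects when the true AUC is below 0.85.** The probability is Φ[(true AUC − cutoff) / √(V(true AUC)/46)]. The values 0.78 to 0.82 are illustrative assumptions.

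| True AUC | (i) null variance | (ii) SE at observed AUC |
|---|---|---|
| 0.72 | 5.0% | 6.6% |
| 0.78 | 28% | 33% |
| 0.80 | 41% | 47% |
| 0.82 | 57% | 63% |
| 0.85 | 80% | 84% |

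**Step 4: what an observed 0.85 would show.** The one-sided 95% lower limit is

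- (i) the value x that solves x + 1.645 · √(V(x)/46) = 0.85: **0.762**
- (ii) 0.85 − 1.645 · √(0.0977/46) = 0.85 − 1.645 · 0.0461 = **0.774**

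**Step 5: what would be needed to support AUC > 0.85 with 46 + 46.** The observed AUC must exceed

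- (i) 0.85 + 1.645 · 0.0461 = **0.926**
- (ii) the x that solves x − 1.645 · √(V(x)/46) = 0.85: **0.910**

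If 0.85 were the null value, 80% power would need about 216 per group at a true AUC of 0.90 and 104 at 0.92 (null variance). These true values are assumptions, because the plan gives no planning value above 0.85.

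**Sensitivity.** With the Hanley-McNeil variance the cutoffs are 0.807 (i) and 0.797 (ii), and the lower limits at an observed 0.85 are 0.769 and 0.783. The conclusion is the same.

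**The case against.** The likeliest explanation is loose notation. The sentence sits in a sample size paragraph, the inputs return 46 only for null value 0.72 and planning value 0.85, and a statistician can recover the intended test from that paragraph. Number of patients, α, power, null value and data set all stay as they are. No passage plans to report a rejection as AUC > 0.85. Section 6 says the study is not being used for regulatory advancement with FDA, and an estimated AUC would let readers see where the result falls relative to 0.85. The rejection rates at 0.78 to 0.82 are the ordinary power curve of a test against 0.72, and those rejections are correct for that test.

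Much of this stands. The design is correctly sized, no operational step depends on the wording, and a cutoff below the planning value is no defect in itself. The harm is a possible over-claim, not a planned one.

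The shorthand reading does not repair the text, however. The plan never calls 0.85 a planning value, says that 46 + 46 are required to test the hypotheses as written, and links them to mammography. If it is shorthand, one sentence corrects it; if it is not, the design cannot support the claim. The attainable accuracy claim also matters to the plan's own purpose: Section 10 (Potential Benefits) looks to a non-invasive diagnosis that would make invasive catheterization unnecessary.

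**Conclusion.** The concern holds and should be fixed. It is an error in how the hypothesis and its interpretation are stated, not in the arithmetic. The stated sample size belongs to a one-sided test of AUC against 0.72, and rejection supports AUC > 0.72 and nothing higher. The gap is material: a result exactly at the mammography benchmark would leave AUCs down to about 0.76 to 0.77 compatible with the data (up to 0.78 with the Hanley-McNeil variance), and a study of a test with true AUC 0.80 would reject in 41% to 47% of cases.

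These figures assume the binormal variance approximation in its usual form, a normally distributed AUC estimate, and 46 patients in each group. The finding that the written alternative is not the tested one depends on none of these.

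**What to change.** In Section 12 (Sample size):

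1. Write H0: AUC ≤ 0.72 against H1: AUC > 0.72, one-sided 5%, with 80% power at a true AUC of 0.85 and 46 + 46 unchanged.
2. Keep mammography only as the reason for choosing 0.85 as the planning value, and reword the opening aim to match.
3. Report the AUC with a one-sided 95% lower limit (or a two-sided 90% interval) by a named method consistent with the test. This also settles which standard error is used.
4. State that rejection does not establish AUC ≥ 0.85 or comparability with mammography.

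If mammography-level accuracy is the claim to be proven, the null value must be set to match it and the study re-sized.

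The recommended change costs one paragraph and one reporting line, with no additional patients. The price is that the permitted claim becomes less favourable.

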### Correlation

Our preliminary Xe MRI studies on patients with PAH, in combination with our previous experience with normals as well as those with other diseases, have helped us formulate quantitative metrics based on Xe MRI studies with high diagnostic potential for PAH. These metrics include the proportion of voxels with low RBC/Gas transfer and the amplitude of the wave seen in Xe MRI based spectroscopy. In Aim 2, our goal is to identify a combination of these metrics which optimally correlates with the current diagnostic standard for PAH which is based on measurements obtained from right heart catheterization, in a training set of 30 patients with and without the disease. The optimal combination will be obtained using discriminant analysis, in which the Xe MRI based metrics will be used as predictors and the diagnosis obtained from right heart catheterization as outcome. To identify the optimal combination and associated thresholds, we will consider all possible combinations of predictors, as well as a variety of discriminant analysis techniques, such as linear discriminant analysis and support vector machines. To avoid optimistic bias from overfitting, we will use leave out one cross validation to obtain an unbiased estimate of prediction error in the training set, which will be used to rank the most predictive discriminant rules. The actual diagnostic accuracy will be evaluated on a separate validation set of 92 patients in Aim 3.

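### Does it matter that the plan never links Aim 3's blinded readers to the discriminant rule that section 12 validates?

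*Combined protocol and SAP*

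**What the plan says.** Section 4 (Design & Procedures) sets out the sequence. In Aim 2, item 2.1 is to "Develop quantification/scoring methods based on PAH, left heart disease, and lung disease MRI", item 2.2 is to "Develop reader training materials and train 3 expert readers", and item 2.3 is to "Begin prospective recruitment of 92 patients undergoing right heart catheterization". In Aim 3, item 3.1 has the trained readers, blinded to disease state, who "will determine the presence and severity of PVD". Item 3.2.1 gives the main focus of Aim 3 as the MRI's "capability to detect absence/presence of pre/post-capillary PH to the gold standard of RHC". It mentions neither readers nor a rule.

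Section 12 (Sample size) states one hypothesis test, on an AUC, with null 0.72 and alternative 0.85, for an ROC curve showing "the tradeoff between sensitivity and specificity for our proposed Xe MRI based diagnostic test". Section 12 (Correlation) then describes a search over metric combinations and discriminant techniques in a training set of 30. Candidate rules are ranked by leave-one-out prediction error. The paragraph closes: "The actual diagnostic accuracy will be evaluated on a separate validation set of 92 patients in Aim 3". Readers are not mentioned in section 12.

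The study design paragraph in section 4 describes the second cohort as "92 subjects who are undergoing right heart catheterization for evaluation of PAH or other cardiac or pulmonary disease. [Aim 2" and gives it that aim's label, whereas section 12 places its evaluation in Aim 3.

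**The concern.** A diagnostic accuracy study should name its index test, and here two candidates apply to the same 92 patients: a computed discriminant score and a reader's judgement. If both produced a result and either could count, the 5% error rate would no longer hold. Two independent tests at 5% would give 1 − 0.95² = 9.75%. If the readers were the intended test, the sample size calculation could not be checked against their output, because neither the reading scale nor the way of combining three reads is given.

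The second worry is order. Recruitment of the 92 begins within Aim 2, the aim in which the rule is developed, and the cohort carries two aim labels. No sentence says that one rule and its thresholds are frozen before the validation labels are linked to the images. If validation data did influence the choice of rule, the AUC from the 92 would be biased upwards.

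**Working it through.** **1. Reproduce the planned size.** Inputs from section 12 (Sample size): null AUC 0.72, alternative 0.85, one-sided 5%, 80% power, one-sample test, binormal variance, equal groups. With A = 1.414 × z(AUC), the binormal variance per patient in each group is

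V = 0.0099 × exp(−A²/2) × [(5A² + 8) + (A² + 8)].

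- AUC 0.72: z = 0.5828, A = 0.824, V = 0.1415, √V = 0.3762.
- AUC 0.85: z = 1.0364, A = 1.466, V = 0.0977, √V = 0.3126.
- n per group = [(1.645 × 0.3762 + 0.8416 × 0.3126) / 0.13]² = [(0.6188 + 0.2631) / 0.13]² = 46.02.
- Power at 46 + 46 = Φ[(0.13 × √46 − 0.6188) / 0.3126] = Φ(0.841) = 79.99%, to rounding.

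The stated 46 + 46 = 92 is therefore what the described method gives for one score on one scale.

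**2. Identify the index test from the text.** The Sample size paragraph tests the AUC of the proposed xenon MRI test and arrives at 92. The Correlation paragraph says how a test is built from the MRI metrics and sends its accuracy to a validation set of 92. The subject, the number and the section are the same. An analyst working from section 12 would take the discriminant score as the variable for the AUC test.

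**3. Place the readers.** Items 2.1, 2.2 and 3.1 run in order: develop the scoring, train readers, have the trained readers evaluate the scans. One natural reading is that the readers apply the scoring, so there is one test. The other is that their judgement is a separate description. Under either reading the AUC test in section 12 can still be carried out as written.

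**4. Check the order of rule and validation.** Section 12 assigns the choice of combination and thresholds to the 30 training patients, ranks rules by cross-validated error within that set, and calls the 92 separate. That already implies selection first and evaluation second. Item 2.3 starts enrolment in Aim 2, and starting enrolment does not open the labels to the developers. The two aim labels are compatible: recruitment starts in Aim 2 and evaluation falls in Aim 3.

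**5. Test the size of the supposed power loss.** Suppose one reader gives a present/absent call from an underlying equal-variance separation with AUC 0.85.

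- Separation d = √2 × 1.0364 = 1.466. The best cut, d/2, gives sensitivity = specificity = Φ(0.733) = 0.768, so the AUC of the call is 0.768.
- Null SE = √(2 × 0.72 × 0.28 / 184) = 0.0468, where 184 = 4 × 46. Alternative SE = √(2 × 0.768 × 0.232 / 184) = 0.0440.
- Power = Φ[(0.0482 − 1.645 × 0.0468) / 0.0440] = 25.6%.

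Now let the call itself meet the plan's alternative, (sensitivity + specificity)/2 = 0.85. The SE is √(2 × 0.85 × 0.15 / 184) = 0.0372, and power = Φ[(0.13 − 1.645 × 0.0468) / 0.0372] = 92.3%.

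The fall to 26% thus comes from lowering the tested AUC from 0.85 to 0.768 as well as from the coarse scale. Simulation using the DeLong standard error gives 33% for the binary call and 91% for a continuous score, but that test rejects about 7% of the time at a true AUC of 0.72. Those figures are not powers at 5% and cannot be set against the planned 80%.

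**The case for a change.** The strongest case for a change is that this is the study's only hypothesis test and its 5% and 80% hold for one score named in advance. No sentence connects item 3.1 with section 12. Two analysts, one starting from section 4 and one from section 12, could report different results as the main one. The search covers all combinations of predictors and several techniques, so a dated record of the chosen rule would be good practice. Writing this down would cost two or three sentences and no patients.

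Part of this stands. The link between readers and rule is unstated, and so is the lock. The single-test reading from items 2.1 and 2.2 is plausible, but it is an inference.

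The consequence does not stand. The inflation to 9.75% needs two independent tests, either of which may count, and the plan specifies one hypothesis and nowhere allows a choice of winner. The power argument needs a binary reader scale, whereas item 3.1 asks for severity as well as presence and the Sample size paragraph describes an ROC tradeoff; both suggest a graded output. Nothing in the text shows validation data reaching rule selection. Making the rule primary and the readers secondary would also demote the one evaluation that Aim 3 describes as blinded. That choice is debatable and belongs to the study team.

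**Conclusion.** No change follows. This is a gap in detail that analysts would fill sensibly: section 12 points to the discriminant score as the test for the AUC hypothesis, restricts its selection to 30 training patients and evaluates it in a separate 92. For that score the sample size is right as stated, at 46.02 per group and 79.99% power, and naming the test or the lock explicitly would alter no figure.

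This rests on two assumptions. Section 12 is taken to govern the hypothesis test, and the separate validation set is taken to be kept separate until the rule is chosen, as its description implies. If the study team meant the readers' judgement to answer the AUC hypothesis, the calculation would have to be revisited for their scale and for variation between readers. The documents do not give the scale, so the illustrative range from 26% to 92% power cannot be narrowed and does not show a fault.
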